4.1.2 Secondary Efficacy Measures

4.1.2.1 Duration of Response

A secondary efficacy objective is to determine the DoR for participants who attain a best confirmed response of PR or CR using BICR MRI volumetric analysis. Confirmed response is defined in Section 4.1.1.

DoR is defined as the time in months between the first instance of response that is subsequently confirmed, until the date of radiographic disease progression or death, whichever occurs first. The DoR will be summarized in months as follows: (date of event (i.e. radiographic disease progression or death) or censoring – date of first response + 1) / 365.25 *12.

For participants who enter the LTFU Phase, all MRI assessments in both the Treatment Phase and LTFU Phase will be used to determine DoR. Those who achieved a DoR of at least 12 months are considered to have experienced a durable response.

Participants without radiographic disease progression or death while on study will have their results censored to their most recent adequate (i.e. evaluable) tumor assessment date.

If participants receive any surgery impacting the target PN or start subsequent systemic therapy for the treatment of PNs prior to radiographic progression, then the participant is censored at the last adequate tumor assessment prior to target PN surgery or subsequent PN treatment. The rules for censoring and events for the duration of response are summarized in Table 5 below.

Table 5: Censoring and Event rules for DoR

Situation	Date of Censoring or Event	Outcome
No adequate tumor assessment post confirmed response	Date of tumor assessment that resulted in response confirmation	Censored
No radiographic disease progression or death post confirmed response	Date of last adequate tumor assessment	Censored
New surgery or subsequent anticancer PN therapy started prior to radiographic disease progression post confirmed response	Date of last adequate tumor assessment before the start of new therapy or surgery	Censored
Two or more consecutive missing or non- adequate tumor assessments post confirmed response	Date of last adequate tumor assessment before the first missing or non-adequate assessment	Censored
Radiographic disease progression that has been verified by BICR post confirmed response	Date of the earliest tumor assessment that results in a finding of progression	Event
Death before radiographic disease progression post confirmed response	Date of death	Event

Document: S:\Q_146\Q_03974\MEK-NF-201\Prog_Stat\Documentation\SAP\MEK-NF-201 SAP v1.0.0.docx

Protocol Number: MEK-NF-201

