4.1.1 Primary Efficacy Measure

The primary efficacy endpoint of interest is the confirmed ORR by the end of Treatment Phase (i.e., Cycle 24). The confirmed ORR is defined as the proportion of participants who have a confirmed ≥ 20% reduction in target tumor volume as compared to baseline as assessed by a BICR, and the response needs to be confirmed by BICR in a consecutive tumor assessment within 2 − 6 months.

To determine the level of target tumor response (complete response [CR], partial response [PR], stable disease [SD], or progressive disease [PD]) which are described below, post-baseline measurement scans are compared to the target PN volume in the pre-treatment MRI scan using volumetric data analysis:

- CR: A complete resolution of the target PN
- PR: A ≥ 20% reduction in the volume of the target PN lesion compared to baseline
- SD: Between a < 20% increase and < 20% decrease in the volume of the target PN lesion compared to baseline
- PD: A ≥ 20% increase in the volume of the target PN compared to baseline. (Radiographic disease progression)

The best overall confirmed response (CR, PR, SD, PD, NE - where SD/PD/NE only require a singular response to be deemed confirmed at that level) will be summarized. For participants that remain on treatment after PD, only the best response up to PD will be considered. For participants who only have one response measurement, and this is a CR or PR (and therefore unconfirmed), their best overall response status will be set to "Missing".

All tumor volume measurements will be independently calculated by two BICR readers. In the case that the two measurements represent different tumor response statuses, as defined above, an independent adjudicator will make the final decision on which response category is recorded at that visit. The primary endpoint analysis will be performed using the adjudicator-selected reader for those visits where the two BICR readers did not agree.

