4.1.2.1.1 Sensitivity Analyses of Duration of Response

According to the Response Evaluation in Neurofibromatosis and Schwannomatosis (REiNS) criteria (Dombi, 2013), progressive disease (PD) is defined as an "increase in the volume of the target lesion by 20% or more compared to baseline or the time of best response after documenting a PR." In order to assess the durability of the response using a similar criterion, the following sensitivity analyses will be performed using the PN volume from the two central readers, separately by each reader:

- DoR applying the REiNS criteria using all scans (I.e. considering scans from both the Treatment Phase and the LTFU phase); defined as the time from the first response which was subsequently confirmed to the derived disease progression scan using BICR PN volume data or death. That is, if a participant had an early confirmed response, a subsequent increase of at least 20% from the confirmed response would not necessarily be considered PD at that timepoint; for example, if the participant had MRI scans showing an even larger shrinkage in target PN volume at later scans, then the largest target PN shrinkage at the later timepoint would be considered the best response when determining PD according to the REiNS criteria.
- DoR applying REiNS using real-time review, defined as the time from first response which was subsequently confirmed to the derived disease progression scan using BICR PN volume data or death considering only the scans up to and including each visit, to assess PD in a real-time review. That is, if a participant had an early confirmed response, a subsequent increase of at least 20% from the confirmed response would be considered PD at that timepoint, regardless of if the participant had MRI scans showing an even larger shrinkage in target PN volume at later scans.

The censoring rules for the sensitivity analyses will be the same as for the main DoR analysis and will follow Table 5.

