6.11.2 Secondary Efficacy Analyses

6.11.2.1 Duration of response for participants whose best response is CR or PR using centrally read MRI volumetric analysis

DoR will be analyzed using Kaplan-Meier (KM) methods, with the median, lower, and upper quartile estimates of DoR and the corresponding 95% Cls (using the Brookmeyer and Crowley method). The number of participants with events (i.e., radiographic disease progression or death) or who are censored, as well as reason for censoring, will be presented separately by age cohort. "NE" will be presented where estimates of such were not estimable. Additionally, KM plots will be presented separately for each age cohort and will contain the number of participants at risk and the event rate. In addition, KM estimates with 95% Cls (using the log-log transformation) will also be presented at key timepoints such as 8, 12, 16, 20, and 24 months.

Censoring rules and the definition of confirmed response are laid out in Section 4.1.2.1.

The sensitivity analyses using REiNS criteria as outlined in Section 4.1.2.1.1 will also be summarized using the same method as described above.

In addition, a swimmer plot will be used to present duration of treatment (in days) where radiographic progression, first onset and confirmation of confirmed response, whether still on study at cutoff and death are displayed, split by cohort.

6.11.2.2 Change from Baseline in quality of life assessed by the age specific Pediatric Quality of Life Inventory

All PedsQL records will be listed by participant, visit and questionnaire type (self-report/parent proxy).

Actual values and change from baseline for each score listed in Section 4.1.2.2.1 will be summarized for each age cohort by visit, for participants overall and by confirmed objective response status (as defined with confirmed response rate in Section 4.1.1 using adjudicated values where appropriate) with self-report and parent proxy scores presented separately. The summaries presented will be number and percentage of participants with a non-missing score, mean, SD, median, minimum, and maximum values.

For PedsQL, a within-patient meaningful score change, or meaningful score difference (FDA, 2023), will be derived by anchor-based analysis of the study's data, as described in the meaningful change threshold analysis plan (Version 1.0, dated 12Sep2023). The primary focus of this will be on if a relevant difference exists at Cycle 13.

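### Is it misleading to call a 12-month duration of response durable when the tumour may be back at its baseline volume?

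*SAP*

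**What the plan says.** SAP 4.1.2.1 runs DoR from the first response that is later confirmed to radiographic progression or death, using scans from both study phases. It then adds the label: "Those who achieved a DoR of at least 12 months are considered to have experienced a durable response".

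SAP 4.1.1 defines progression as "A ≥ 20% increase in the volume of the target PN compared to baseline" and stable disease as "Between a < 20% increase and < 20% decrease in the volume of the target PN lesion compared to baseline". A tumour at exactly its baseline volume is therefore stable disease.

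In Table 5 the row "No radiographic disease progression or death post confirmed response" leads to censoring at the last adequate scan. No row makes loss of partial response an event or a reason for censoring.

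SAP 4.1.2.1.1 cites the REiNS definition, under which a 20% increase counts from baseline or, after a partial response, from best response. It adds two analyses for each central reader, with the purpose "In order to assess the durability of the response using a similar criterion". In the all-scans version, a 20% rise after an early confirmed response "would not necessarily be considered PD at that timepoint" if deeper shrinkage follows. In the real-time version the same rise "would be considered PD at that timepoint, regardless of if the participant had MRI scans showing an even larger shrinkage".

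SAP 6.11.2.1 analyses DoR by Kaplan-Meier, with estimates that "will also be presented at key timepoints such as 8, 12, 16, 20, and 24 months", and applies the same method to the REiNS analyses. It lists no count of durable responders.

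**The concern.** In ordinary use a durable response means shrinkage that lasted. The label in 4.1.2.1 requires only that the tumour has not grown 20% beyond its starting size, so a participant with no remaining shrinkage can qualify, and the section does not say so. The next subsection uses durability in a different sense, measured from best response, so the same participant can be durable under one rule and not under the other.

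The protocol calls the study potentially registrational (Protocol 9.2) and names DoR among its key secondary endpoints (Protocol 4.1). A statement that some proportion of responders had durable responses could be read as more than the definition supports.

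**Working it through.** **Inputs.** Scan days from SAP Table 12: C5 = 127, C9 = 239, C13 = 351, C17 = 463, C21 = 575, C24 = 665. DoR in months = (end day − first response day + 1)/365.25 × 12 (SAP 4.1.2.1). Partial response is a volume of at most 0.80 of baseline and main progression is at least 1.20 (SAP 4.1.1). Growth rates of 21.1% and 8.4% a year come from the observational study of 49 patients described in Protocol 4.2.

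**1. Can the main DoR pass 12 months at baseline volume?** Yes.

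| Trajectory | Main DoR, no event | Real-time REiNS event |
|---|---|---|
| Response C5, confirmed C9, at baseline from C13 | at C21: 449/365.25 × 12 = 14.75 | at C13: 225/365.25 × 12 = 7.39 |
| Response C9, confirmed C13, at baseline from C17 | at C24: 427/365.25 × 12 = 14.03 | at C17: 225/365.25 × 12 = 7.39 |

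For a C5 responder, C17 gives 337/365.25 × 12 = 11.07 months, so C21 is the first scheduled scan past 12 months.

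**2. Does a planned analysis detect it?** A return to baseline from a partial response is a rise of at least 1/0.80 = 1.25 from nadir, above the REiNS factor of 1.20. The real-time version therefore has an event no later than the first scan back at baseline. The all-scans version gives the same event in both trajectories above and can differ only if deeper shrinkage comes later.

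**3. How fast must the tumour regrow?**
- First trajectory: from at most 0.80 at C9 to 1.00 at C13 is at least +25% in 112 days. That is 0.25 × 365.25/112 = 82% a year linear, or 1.25^(365.25/112) − 1 = 107% compounded.
- Gradual version: 0.80 at C9 and 1.00 by C21 (336 days) needs 0.25 × 365.25/336 = 27.2% a year linear, or 27.5% compounded.
- At 21.1% a year, 0.80 at C9 becomes 0.80 × (1 + 0.211 × 336/365.25) = 0.955 at C21. For a C9 responder, 0.80 at C13 becomes 0.80 × (1 + 0.211 × 314/365.25) = 0.945 at C24. Neither is back at baseline.

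**4. When do the two rules disagree at 12 months?** Take a C5 responder regrowing from a C5 nadir. REiNS denies 12 months only if the rise reaches 20% by C17, 336 days later. That needs 0.20 × 365.25/336 = 21.7% a year linear, or 1.2^(365.25/336) − 1 = 21.9% compounded. At 21.1% the rise by C17 is 19.4% (19.3% compounded), so the REiNS event falls at C21 (+25.9% or +26.5%), at 14.75 months, and both rules exceed 12 months. At 8.4% the rise by C21 is only 10.3% to 10.4%.

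**5. Would a REiNS 12-month count show whether shrinkage lasted?** Only partly.
- The REiNS threshold is 1.2 × (1 − s) of baseline for a nadir shrinkage s. This is 0.96 at s = 20%, 0.80 at s = 33.3% and 0.72 at s = 40%.
- A shallow responder can lose its partial response without being flagged. With a C5 nadir of 0.751, just deep enough to be confirmed at C9 at 21.1% a year (0.751 × 1.065 = 0.80), the volume at C21 is about 0.95 of baseline, yet both rules put DoR at 14.75 months or more.
- A responder deeper than 33.3% can be flagged while still in partial response.
- A raw count also handles censoring poorly. A C13 responder last scanned at C24 is censored at 315/365.25 × 12 = 10.35 months. Kaplan-Meier uses that follow-up, but a count must call the participant not durable or drop the record.

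**The case for a change.** The best case for a change is that it is cheap: one sentence in 4.1.2.1 would remove the ambiguity, and a 12-month count under the real-time REiNS rule needs no new data. A label without a specified output also leaves its presentation to be settled at reporting. The planned REiNS analyses use each reader's volumes, so they do not sit exactly beside the adjudicated responders, and only the real-time version is certain to register a return to baseline. The cited growth rates are observational, so they cannot exclude faster regrowth in a responder.

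Some of this stands. The label is looser than everyday usage, and 4.1.2.1 does not spell that out. But the sentence would only join up 4.1.1 and Table 5, whose rule also matches Protocol 7.1 and 10.7. The added count would have the same reader-specific denominators as the planned curves and would handle censoring less well. It would also need a caveat of its own for deep responders. Loss of shrinkage will be visible in any case: 6.11.3.6 summarises volume and percentage change by visit, and 6.11.1 lists all MRI tumour data from both phases.

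**Conclusion.** The algebra of the concern is right, but no change to the plan is needed. The 12-month label means freedom from baseline-referenced progression and from death for 12 months after first response. That follows from the stated definitions without contradiction. Durability from best response is already estimated, with Kaplan-Meier figures at 12 months for each reader, and an author who describes durable responses in the study report can cite those beside the main result.

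The possible discrepancy is 14.75 or 14.03 months against 7.39 in the constructed trajectories. For a C5 responder regrowing steadily from a C5 nadir, the two rules part at 12 months only from about 22% a year, just above the faster cited rate of 21.1%. This rests on scans at the nominal days, steady regrowth and observational rates that were not measured after a response on treatment. The number of participants affected cannot be known from the documents. DoR is secondary and carries no hypothesis test, and a clearer sentence would alter no estimate, so this is missing explanation with no analytic gain from adding it.

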4.1.2.1.1 Sensitivity Analyses of Duration of Response

According to the Response Evaluation in Neurofibromatosis and Schwannomatosis (REiNS) criteria (Dombi, 2013), progressive disease (PD) is defined as an "increase in the volume of the target lesion by 20% or more compared to baseline or the time of best response after documenting a PR." In order to assess the durability of the response using a similar criterion, the following sensitivity analyses will be performed using the PN volume from the two central readers, separately by each reader:

- DoR applying the REiNS criteria using all scans (I.e. considering scans from both the Treatment Phase and the LTFU phase); defined as the time from the first response which was subsequently confirmed to the derived disease progression scan using BICR PN volume data or death. That is, if a participant had an early confirmed response, a subsequent increase of at least 20% from the confirmed response would not necessarily be considered PD at that timepoint; for example, if the participant had MRI scans showing an even larger shrinkage in target PN volume at later scans, then the largest target PN shrinkage at the later timepoint would be considered the best response when determining PD according to the REiNS criteria.
- DoR applying REiNS using real-time review, defined as the time from first response which was subsequently confirmed to the derived disease progression scan using BICR PN volume data or death considering only the scans up to and including each visit, to assess PD in a real-time review. That is, if a participant had an early confirmed response, a subsequent increase of at least 20% from the confirmed response would be considered PD at that timepoint, regardless of if the participant had MRI scans showing an even larger shrinkage in target PN volume at later scans.

The censoring rules for the sensitivity analyses will be the same as for the main DoR analysis and will follow Table 5.

4.1.2.2 Patient-Reported Outcomes (PROs)

Additional secondary efficacy objectives focus on the impact of mirdametinib on participant quality of life (QoL) and pain using the following PROs:

- Pediatric Quality of Life Inventory (PedsQL)
- Numeric Rating Scale-11 (NRS-11)
- Pain Interference Index (PII).

4.1.2.2.1 Pediatric Quality of Life Inventory (PedsQL)

The PedsQL 4.0 Generic Core Scales are multidimensional self-report and parent proxy-report scales to assess health-related quality of life (HRQoL) in children, adolescents, young adults, and adults with a recall period of 7 days. It is a brief standardized HRQoL scale with good reliability and validity. It consists of a 23-item core measure of global QoL and can be completed in approximately 5 minutes. The questions are split into four dimensions, each of which can have an overall scale score calculated.

The secondary endpoint Change from baseline in quality of life (QoL) assessed by the age specific Pediatric Quality of Life Inventory will be evaluated using the following PedsQL scores:

- Physical functioning,
- Emotional functioning,

Document: S:\Q 146\Q 03974\MEK-NF-201\Prog Stat\Documentation\SAP\MEK-NF-201 SAP v1.0.0.docx

Author:

- Social functioning,
- School/work functioning,
- Total score.

PedsQL items are answered on a Likert scale with responses ranging from 0 to 4 (where 0 means it is never a problem and 4 means it is almost always a problem). These items are then reverse scored and linearly transformed to a 0-100 scale as follows: 0=100, 1=75, 2=50, 3=25, 4=0. Overall scale scores are calculated as the mean of the scores for the questions in said scale (or of all questions for the total score).

Participants complete PedsQL at the time points specified in the SoA (Sections 1.3-1.4 of the protocol).

4.1.2.2.2 Numerical Rating Scale=11 (NRS-11)

The NRS-11 is a self-report segmented 11-point numeric scale that assesses pain severity over the past 24 hours. The NRS-11 is administered daily over 7 consecutive days, inclusive of the study visit day, during the Treatment Phase as described in the SoA (Sections 1.3-1.4 of the protocol). For the ET visit, the assessment is only conducted once at the site and not for the preceding 6 days. Participants ≥ 8 years of age are administered the NRS-11 as a self-report.

Participants are asked to select the one number from 0 to 10 that best describes their worst pain over the past 24 hours for target tumor pain with 0 representing "no pain" and 10 representing "worst pain you can imagine". The NRS-11 score presented each visit will be taken as the average of the responses over the 7 consecutive days leading up to and including the visit day, with no transformation applied. The scale is presented in Appendix 1.3.

4.1.2.2.3 Pain Interference Index (PII)

The PII assesses self-reported consequences of pain on relevant aspects of one's life over the past 24 hours. The PII will be administered daily over 7 consecutive days, inclusive of the study visit day, as described in the SoA (Sections 1.3-1.4 of the protocol). For the ET visit, the assessment is only conducted once at the site and not for the preceding 6 days. Pain interference refers to the degree to which pain interferes with or limits an individual's daily activities. The PII also incorporates items probing sleep and mood. The PII is universal rather than disease specific. All participants ≥ 6 years of age complete the PII as a self-report during the Treatment Phase. Parents or legal guardians of children from 6 to 17 years of age will complete the parent proxy PII in parallel.

The PII consists of 6 questions, each asking the responder to select one number from 0 to 6 that best describes how their/their proxy's pain has impacted various items over the past 24 hours with 0 representing "Not at all" and 6 representing "Completely". The mean of the completed items is taken as the PII score for a single assessment. The PII score presented each visit will be taken as the average of the PII scores over the 7 consecutive days up to and including visit day, with no transformation applied. The full questionnaire is presented in Appendix 1.4.

4.1.3 Exploratory Efficacy Measures

4.1.3.1 Patient-Reported Outcomes Measurement Information System (PROMIS) – Physical Function/Mobility/Upper Extremity Scale

The PROMIS Physical Function instruments measure self-reported capability rather than actual performance of physical activities. This includes the functioning of one's upper extremities (dexterity), lower extremities (walking or mobility), and central regions (neck, back), as well as instrumental activities of daily living, such as running errands. A single Physical Function capability score is obtained from each short form. This PRO is only completed during the Treatment Phase.

All participants in the adult cohort with a target PN causing significant physical functioning impairment at baseline should complete the PROMIS Short Form v2.0 – Physical Function 8b. For all participants in the pediatric cohort, the questionnaire will be specific to the location of the target PN, either PROMIS Pediatric Short Form v2.0 – Upper Extremity 8a or PROMIS Pediatric Short Form v2.0 – Mobility 8a. Pediatric participants of age ≥ 5 will also have a parent proxy version of the relevant form completed by an adult caregiver. Further details of the assessment of PROMIS can be found in the Section 8.1.2.3 of the protocol.

All PROMIS items are answered on a Likert scale with responses ranging from 1 to 5, with higher scores representing higher reported physical capability. For each PROMIS Scale, a total raw score will be calculated as the sum of the individual item responses at a given visit (total raw scale range 8-40). The total raw scores for the measure will be converted to T-scores using the applicable score conversion table in the user manual and scoring instructions (PROMIS, 2023). All items must be answered to produce a valid score using the scoring tables. A higher T-score indicates better reported physical capability.

Participants complete the applicable PROMIS Physical Function instrument at the time points specified in the SoA (Section 1.3 of the protocol).

